10.3.1 Variables and Criteria Defining Abnormality

The liver-specific laboratory tests include the serum glutamic pyruvic transaminase (SGPT/ALT), serum glutamic-oxaloacetic transaminase (SGOT/AST), alkaline phosphatase, and total bilirubin.

The number and percentage of subjects meeting the criteria for potentially clinically significant liver function laboratory values will be summarized and a listing of potentially clinically significant liver function laboratory values will be provided. The table and listing will include all subjects who met any of the following 4 criteria:

ALT $\geq 3 \times$ ULN, or
AST $\geq 3 \times$ ULN, or
Alkaline phosphatase $\geq 1.5 \times$ ULN, or
Total bilirubin $\geq 2 \times$ ULN.

A listing of potential Hy's Law cases, defined as those who meet all of the following conditions will be provided.

- ALT of $> 3 \times \text{ULN}$ or AST of $> 3 \times \text{ULN}$,
- associated with an increase in bilirubin $\geq 2 \times \text{ULN}$.

Additional listing of patients who met all of the following 3 criteria will be provided:

- ALT of $> 3 \times \text{ULN}$ or AST of $> 3 \times \text{ULN}$,
- associated with an increase in bilirubin $\geq 2 \times \text{ULN}$,
- Alkaline phosphatase $< 2 \times \text{ULN}$.

10.3.2 Statistical Methods

Changes from baseline in continuous laboratory parameters will be summarized by n, mean, standard deviation, minimum value, median, and maximum value for each treatment group.

Shift tables from baseline to the final value (the last assessment during each treatment period) according to the normal range will be provided for each hematology, clinical chemistry parameter and urinalysis parameter. The laboratory data will be categorized as low, normal, or high based on the normal ranges of the central laboratory used in this study. The shift tables will tabulate the number and percentage of subjects with baseline values below/within/above the normal range versus final values below/within/above the normal range.

For selected laboratory parameter with Common Toxicity Criteria (CTC) a listing of all subjects with any laboratory determinations meeting CTC Grade ≥ 3 as well as being a higher grade than the baseline CTC grade will be provided. For each of these subjects, the whole course of the parameter of the current study along with the baseline value will be listed.

Pre-defined criteria of CTC Grade 3 or greater are given in [Table 8](#) and [Table 9](#) below for selected chemistry variables and hematology variables respectively based on CTC Version 4.0. Please refer to Appendix [12.8](#) for the CTC Grades 1 - 4 for these variables based on CTC Version 4.0.

Table 8. Criteria for CTC Grade 3 or Greater for Chemistry Values

Chemistry Variables	Units	Definition of CTC Grade 3 or Greater	
		Very Low	Very High
TBL	mcmol/L		> 3.0 × ULN
SGOT/AST	U/L		> 5.0 × ULN
SGPT/ALT	U/L		> 5.0 × ULN
Albumin	g/L	< 20	
Glucose	mmol/L	< 2.2	> 13.9
Triglycerides	mmol/L		> 5.7
Creatinine	mcmol/L		> 3.0 × ULN
Sodium	mmol/L	< 130	> 155
Potassium	mmol/L	< 3.0	> 6.0
Calcium	mmol/L	< 1.75	> 3.1
CPK	U/L		> 5.0 × ULN
Total Cholesterol	mmol/L		> 10.34
GGT			> 5.0 × ULN
ALP			> 5.0 × ULN

Table 9. Criteria for CTC Grade 3 or Greater for Hematology Values

Hematology Variables	Units	Definition of CTC Grade 3 or Greater	
		Very Low	Very High
Hemoglobin	g/L	< 80.0	
Platelets count	10 ⁹ /L	< 50.0	
WBC count	10 ⁹ /L	< 2.0	
Neutrophils	10 ⁹ /L	< 1.0	
Lymphocytes	10 ⁹ /L	< 0.5	

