7.3.3 Safety analyses

Since the main objective of this study is long term safety, the primary focus would be on incidence of drug-related AE and serious infection.

Adverse events will be coded using the Medical Dictionary for Regulatory Activities (MedDRA) coding dictionary. Summary tables and listings will be produced. All adverse events with an onset between start of treatment and end of the residual effect period (REP), a period of 20 weeks after the last dose of trial medication, will be assigned to the treatment period for evaluation.

All treated patients will be included in the safety analysis.

Statistical analysis and reporting of adverse events will concentrate on treatment-emergent adverse events. To this end, all adverse events occurring between start of treatment and end of the residual effect period will be considered 'treatment-emergent'. Adverse events that start before first drug intake and deteriorate under treatment will also be considered as 'treatment-emergent'. Frequency, severity, and causal relationship of adverse events will be tabulated by system organ class and preferred term after coding according to the current version of the Medical Dictionary for Drug Regulatory Activities (MedDRA). Safety analyses will focus on adverse events related to early discontinuation, immune suppression and injection site effects.

Laboratory data will be analysed both quantitatively as well as qualitatively. The latter will be done via comparison of laboratory data to their reference ranges. Values outside the reference range as well as values defined as clinically relevant will be highlighted in the listings. Treatment groups will be compared descriptively with regard to distribution parameters as well as with regard to frequency and percentage of patients with abnormal values or clinically relevant abnormal values. Analysis of laboratory measures will focus on haemotologic measures of immune suppression.

Vital signs, physical examinations, or other safety-relevant data observed at screening, baseline, during the course of the trial and at the end-of-trial evaluation will be assessed with regard to possible changes compared to findings before start of treatment.

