12.8 Common Toxicity Criteria (CTC) Grade for Laboratory Data

Test	Grade 1	Grade 2	Grade 3	Grade 4
Chemistry Variables				
SGPT/ALT increased	> ULN – 3.0 × ULN	> 3.0 – 5.0 × ULN	> 5.0 – 20.0 × ULN	> 20.0 × ULN
SGOT/AST increased	> ULN – 3.0 × ULN	> 3.0 – 5.0 × ULN	> 5.0 – 20.0 × ULN	> 20.0 × ULN
GGT increased	> ULN – 2.5 × ULN	> 2.5 – 5.0 × ULN	> 5.0 – 20.0 × ULN	> 20.0 × ULN
ALP increased	> ULN – 2.5 × ULN	> 2.5 – 5.0 × ULN	> 5.0 – 20.0 × ULN	> 20.0 × ULN
TBL increased	> ULN – 1.5 × ULN	> 1.5 – 3.0 × ULN	> 3.0 – 10.0 × ULN	> 10.0 × ULN
Creatinine increased	> ULN – 1.5 × ULN	> 1.5 – 3.0 × ULN	> 3.0 – 6.0 × ULN	> 6.0 × ULN
CPK increased	> ULN – 2.5 × ULN	> 2.5 – 5.0 × ULN	> 5.0 – 10.0 × ULN	> 10.0 × ULN

Test	Grade 1	Grade 2	Grade 3	Grade 4
Chemistry Variables				
Total Cholesterol increased	> ULN - 7.75	> 7.75 - 10.34	> 10.34 - 12.92	> 12.92
Albumin decreased	< LLN - 30	< 30 - 20	< 20	N/A
Triglycerides increased	1.71 - 3.42	> 3.42 - 5.7	> 5.7 - 11.4	> 11.4
Glucose	< LLN - 3.0 or > ULN - 8.9	< 3.0 - 2.2 or > 8.9 - 13.9	< 2.2 - 1.7 or > 13.9 - 27.8	< 1.7 or > 27.8
Sodium	< LLN - 130 or > ULN - 150	> 150 - 155	< 130 - 120 or > 155 - 160	< 120 or > 160
Potassium	< LLN - 3.0 or > ULN - 5.5	< LLN - 3.0 or > 5.5 - 6.0	< 3.0 - 2.5 or > 6.0 - 7.0	< 2.5 or > 7.0
Calcium	< LLN - 2.0 or > ULN - 2.9	< 2.0 - 1.75 or > 2.9 - 3.1	< 1.75 - 1.5 or > 3.1 - 3.4	< 1.5 or > 3.4
Hematology Variables				
Hemoglobin decreased	< LLN - 100.0 g/L	< 100.0 - 80.0 g/L	< 80.0 g/L	N/A
Neutrophil count decreased	< LLN - $1.5 \times 10^9/L$	< 1.5 - $1.0 \times 10^9/L$	< 1.0 - $0.5 \times 10^9/L$	< $0.5 \times 10^9/L$
WBC decreased	< LLN - $3.0 \times 10^9/L$	< 3.0 - $2.0 \times 10^9/L$	< 2.0 - $1.0 \times 10^9/L$	< $1.0 \times 10^9/L$
Lymphocyte count decreased	< LLN - $0.8 \times 10^9/L$	< 0.8 - $0.5 \times 10^9/L$	< 0.5 - $0.2 \times 10^9/L$	< $0.2 \times 10^9/L$
Platelets count decreased	< LLN - $75.0 \times 10^9/L$	< 75.0 - $50.0 \times 10^9/L$	< 50.0 - $25.0 \times 10^9/L$	< $25.0 \times 10^9/L$

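### Haematology abnormality is tabulated only at the last assessment of each treatment period, so a transient low count enters no SAP-specified patient frequency unless it is reported as an adverse event

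*SAP*

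**What the plan says.** Long-term safety is the primary objective (Protocol 2.2; SAP 4.1).

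- **Protocol 7.3.3** says laboratory data will be described "with regard to frequency and percentage of patients with abnormal values or clinically relevant abnormal values". It directs the laboratory analysis to haematologic measures of immune suppression, and says out-of-range and clinically relevant values will be highlighted in listings. It does not say whether the frequencies refer to any visit or to the last one.
- **SAP 10.3.2** gives three outputs for haematology. The first is change from baseline, summarised by n, mean, SD, minimum, median and maximum. The second is the shift table: "Shift tables from baseline to the final value (the last assessment during each treatment period) according to the normal range will be provided". The third is "a listing of all subjects with any laboratory determinations meeting CTC Grade ≥ 3 as well as being a higher grade" than at baseline. For that listing, "For each of these subjects, the whole course of the parameter of the current study along with the baseline value will be listed".
- **SAP Table 9**, "Criteria for CTC Grade 3 or Greater for Hematology Values", sets the listing thresholds. SAP 12.8 gives Grades 1 to 4.
- **SAP 10.3.1** tabulates the number and percentage of subjects who meet any of four liver criteria, and **SAP 10.4.2** does the same for vital-sign criteria. Neither is tied to the final value.
- **SAP 6.5** says that all values are considered for shift summaries. The sentence stands under the rule for several measurements on the same day.

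**The concern.** A shift to the last value describes status at the end of a period. It does not show whether a patient had a low count at some point during treatment. In a long-term safety study whose protocol names haematologic immune suppression as the laboratory focus, the second question is the one a reader will ask. As written, the report can state how many patients ever crossed a liver threshold. It cannot state how many ever had a low neutrophil or lymphocyte count, except through adverse event reporting or by hand-counting a Grade 3 listing.

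**Working it through.** **1. Where a transient low haematology value would appear**

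| Output | Values used | n (%) of patients? | Shows a transient low value? |
|---|---|---|---|
| Change from baseline (SAP 10.1, 10.3.2) | By visit; minimum given | No | An extreme drop may show in the minimum; no patient is counted |
| Shift table (SAP 10.3.2) | Last of each period | Yes | Only if still low at the last assessment |
| Grade 3+ listing (SAP 10.3.2) | Any determination | No | Only at Grade 3+ and above the baseline grade |
| TEAE tables (SAP 10.2.1.2, 10.2.1.3) | Any time on treatment | Yes | Only if reported as an AE |
| Listings (Protocol 7.3.3) | Out-of-range values | No | Highlighted, not counted |
| Liver tests, for comparison (SAP 10.3.1) | Any qualifying value | Yes | Yes |
| Vital signs, for comparison (SAP 10.4.2) | Any qualifying value | Yes | Yes |

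Under Protocol 5.2.2.1 a laboratory abnormality is an AE only if it leads to discontinuation or intervention, or if the investigator regards it as one. Protocol 5.2.2.2 has laboratory changes recorded as AEs when they are judged clinically relevant.

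**2. The range that the listing does not reach.** Grade 3 starts below 1.0 (neutrophils), 0.5 (lymphocytes), 2.0 (WBC) and 50 (platelets), all x10^9/L, and below 80 g/L (haemoglobin). From the lower limit of normal down to those values (the Grade 1-2 columns of SAP 12.8, for example in the row "Neutrophil count decreased") no SAP-specified count or subject listing applies. The grading scale also matters for lymphocytes. The RCTC table in Protocol Appendix 10.3 puts 0.5-0.9 in Grade 3, while the SAP's CTC Grade 3 starts below 0.5. A count of 0.6 is therefore severe on the protocol's scale and outside the SAP listing.

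**3. Number of visits, K**
- SAP Table 1 has post-baseline SC windows at week 8, at weeks 16 to 192 in steps of 8 (i = 2 to 24, so 23 windows) and at week 200: 1 + 23 + 1 = 25.
- Flow Chart 1 has Visits 3 to 27 plus EoT: 25 + 1 = 26.
- For shorter follow-up, the top exposure category in SAP 8.2.1 starts above 924 days: 924/56 = 16.5, so about 16 eight-week intervals. This case is needed because the rationale for Amendment 4 says the study will be terminated and treatment durations will differ.

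**4. Chance that the final value catches a one-visit dip.** If the dip is equally likely at each of K visits, the probability is 1/K:
- K = 26: 1/26 = 3.8%
- K = 25: 1/25 = 4.0%
- K = 16: 1/16 = 6.3%

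For a dip spanning three visits the answer depends on an assumption. If the whole episode must lie within 26 visits there are 24 placements and one includes the last visit: 1/24 = 4.2%. If episodes may be cut off at the end of the study: 3/26 = 11.5%.

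This concerns the SC period. SAP Table 6 has only two post-dose windows in the IV period, so much less can be lost there.

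**5. Illustration in patients.** N = 60 is the planned number. The documents give no rate of low counts, so the per-visit probability p is assumed, with visits independent. Expected patients low at the final value = 60p. Expected patients ever low = 60 x [1 - (1 - p)^K].

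| p per visit | Low at final value | Ever low, K = 16 | Ever low, K = 25 |
|---|---|---|---|
| 0.5% | 0.3 | 4.6 | 7.1 |
| 1% | 0.6 | 8.9 | 13.3 |
| 2% | 1.2 | 16.6 | 23.8 |

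If low counts cluster in the same patients, the ever-low columns are too high.

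**The case against.** There is a fair case for the SAP as it stands.

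- **Severe falls are reported.** The listing takes any determination at Grade 3 or higher and prints the full course. With about 60 patients a reader can count the lines.
- **The protocol's wording is met in part.** The shift tables do give numbers and percentages low, normal and high for every haematology parameter, and Protocol 7.3.3 does not say at any visit.
- **Clinically relevant falls are counted.** They are recorded as AEs and tabulated by preferred term and maximum severity.
- **Mild low counts are hard to interpret.** There is no comparator, and Protocol 4.2.2.1 allows stable azathioprine, 6-mercaptopurine, methotrexate and oral corticosteroids.

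All four stand, and they rule out stronger readings that a reader might infer. One is that a severe transient neutropenia would vanish from the report; the Grade 3 listing contradicts this. A second is that the SAP plainly breaches Protocol 7.3.3, whose wording leaves the time point open. A third is that the shift table gives a biased incidence, although the SAP never presents it as an estimate of incidence. A fourth is that Grade 1-2 values appear nowhere at all, although the protocol promises highlighted listings.

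These points do not close the gap. The listing stops at Grade 3, AE reporting depends on the investigator's judgement, and highlighted listings count nobody. SAP 6.5 does not help either, because its sentence on using all values concerns same-day repeats and the final-value rule in SAP 10.3.2 is explicit.

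**Conclusion.** The point holds as a reporting gap in the primary-objective analysis. It does not invalidate the study. SAP 10.3.2 provides no patient frequency for low haematology values on treatment other than at the last assessment, while liver tests and vital signs have one. Transient values at Grade 3 or higher and above the baseline grade are listed without n (%). Transient Grade 1-2 values depend on AE reporting to be counted at all.

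Under the equal-chance assumption, the final-value table would miss about 94% to 96% of one-visit dips. How many patients that means cannot be said from the documents, because they give no cytopenia rate; the patient counts above rest on assumed rates and independent visits. The change should be made because it is cheap and serves the focus that the protocol itself sets.

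**What to change.** Keep the final-value shift table. Add to SAP 10.3.2, for neutrophils, lymphocytes, WBC, platelets and haemoglobin:

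1. a shift table from baseline to the worst (lowest) post-baseline value;
2. n (%) of subjects by worst post-baseline CTC grade, showing at least Grade 2 or higher and Grade 3 or higher.

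Produce both for these intervals:

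- **IV period:** first IV dose to the earlier of last IV dose + 140 days and first SC dose.
- **SC period:** first SC dose to the earlier of last SC dose + 140 days and first dose in M16-000 Sub-Study 3.
- **All risankizumab:** first dose in this study to the earlier of last dose + 140 days and first dose in M16-000 Sub-Study 3.

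The caps are needed. In Flow Chart 3 the last infusion is at week 12 and the first SC dose at week 16, which is 28 days later. An uncapped 140-day window would therefore bring up to 140 - 28 = 112 days of SC-period values into the IV table. The SAP already cuts off at these points in Table 1 (note b), 7.3 and 10.2.1.7.

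Also state in SAP 6.5 that the sentence on considering all values applies to same-day repeats.

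The cost is programming only, since the measurements are already scheduled at the treatment visits. The downside is that the worst of many measurements shows more chance excursions and there is no comparator. Presenting the worst-value and final-value tables together lets the reader see which falls persisted.

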6.0 Analysis Conventions

6.1 Definition of Baseline

Efficacy analysis:

For efficacy analysis, the baseline is defined as the last measurement prior to the first dose of the study drug in the feeder Study M15-993 (1311.6).

Safety analysis:

For safety analyses, the baseline is defined as the last measurement prior to the first dose of risankizumab in the feeder Study M15-993 (1311.6).

Demographics and Baseline Characteristics:

For Demographics and Baseline Characteristics, the data will be from the baseline of the feeder Study M15-993 (1311.6).

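### The CTC Grade 3+ laboratory listing omits a patient who was Grade 3 at the pre-risankizumab feeder baseline, recovered, and returned to Grade 3 in M15-989; another laboratory listing covers only 4 of the 19 parameters

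*SAP*

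**What the plan says.** SAP 10.3.2 plans a listing of subjects with any laboratory value at CTC Grade 3 or higher "as well as being a higher grade than the baseline CTC grade". It applies to the 14 chemistry parameters of Table 8 and the 5 haematology parameters of Table 9. For a listed subject, the full M15-989 course of that parameter is printed with the baseline value.

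For safety analyses, SAP 6.1 states that "the baseline is defined as the last measurement prior to the first dose of risankizumab in the feeder" study, M15-993. The value at entry to the extension plays no part in the rule.

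SAP 12.8 gives the grade limits in four columns, Grades 1 to 4. Two rows end without a Grade 4: "Hemoglobin decreased < LLN - 100.0 g/L < 100.0 - 80.0 g/L < 80.0 g/L N/A" and "Albumin decreased < LLN - 30 < 30 - 20 < 20 N/A".

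The other laboratory outputs in SAP 10.3 are these:
- summaries of change from baseline (10.3.2);
- shift tables by normal range, from baseline to the last value in each treatment period (10.3.2);
- a table and listings of liver tests by multiples of the upper limit of normal (10.3.1).

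None of these uses CTC grades.

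**The concern.** Long-term safety is the primary objective, and Protocol 7.3.3 says laboratory analysis will concentrate on haematological signs of immune suppression. In about 60 patients, a listing of severe values is the output in which a single case can be seen.

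The reference point matters in this population. The feeder baseline precedes risankizumab. Entry to the extension requires clinical response or remission in the feeder study (Protocol 3.3.2), and haematocrit is a scored component of the CDAI (SAP 12.1). Recovery of an abnormal value between the two points is therefore a plausible course. A later return to Grade 3 on long-term treatment is something a safety reader would want to see, and the rule removes it because the patient had already been at that grade before any drug.

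**Working it through.** No sample size or error rate is involved. The check applies the listing rule to the grade table.

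**Inputs.** Rule: listed if grade ≥ 3 and grade > baseline grade (SAP 10.3.2). Baseline: last value before risankizumab in the feeder study (SAP 6.1). Parameters: 14 (Table 8) + 5 (Table 9) = 19. The Table 8 and 9 cut-offs, 10 low and 13 high, all agree with the Grade 3 limits in SAP 12.8.

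**Which on-study grades lead to listing**

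| Baseline grade | 17 parameters with a Grade 4 | Haemoglobin, albumin |
|---|---|---|
| 0, 1 or 2 | 3 or 4 | 3 |
| 3 | 4 only | none |
| 4 | none | not applicable |

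**Haemoglobin examples** (Grade 2 below 100 g/L, Grade 3 below 80 g/L)

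| Feeder baseline | M15-989 value | Grades | Listed? |
|---|---|---|---|
| 110 g/L | 75 g/L | at most 1, then 3 | yes |
| 95 g/L | 75 g/L | 2, then 3 | yes |
| 78 g/L | 75 g/L | 3, then 3 | no |
| 78 g/L | 60 g/L | 3, then 3 | no |
| 78 g/L | 40 g/L | 3, then 3 | no |

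The last three results do not change if the patient stood at, say, 125 g/L on entering the extension, because the rule never looks at that value.

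**Do the other laboratory outputs show the case?**
- *Liver listing (SAP 10.3.1).* It has no baseline condition, and its cut-offs lie below Grade 3: ALT and AST ≥ 3 against > 5 × ULN, ALP ≥ 1.5 against > 5 × ULN, total bilirubin ≥ 2 against > 3 × ULN. It catches every Grade 3 value of these four tests. The gap is therefore 19 − 4 = 15 parameters: 13 in which a Grade 3 baseline leaves only Grade 4 listable, and 2 in which it leaves nothing listable. All five parameters of Table 9 are among the 15.
- *Shift tables.* They use the feeder baseline and the last value only. A temporary fall does not appear, and if the low value is the last one, the patient is counted as low to low.
- *Change from baseline.* For a course of 78, 125, then 75 g/L, the change reported is 75 − 78 = −3 g/L, whereas the fall since extension entry is 75 − 125 = −50 g/L. The minimum in the summary could reflect a deeper fall, but it does not identify the patient.

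**The case against.** **A drug-free baseline is a coherent choice.** Requiring a grade above the pre-drug state is a recognised way to define worsening, and the SAP combines absolute limits with change from baseline for vital signs as well (Table 10). This stands. The patient in question had the same grade before any risankizumab, so the event is a relapse and not a first occurrence. The drug-free baseline should be kept. The weakness is that it alone decides whether a severe value is listed.

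**The adverse-event route.** A laboratory abnormality is an adverse event if it leads to discontinuation, needs treatment, or is considered one by the investigator (Protocol 5.2.2.1). Clinically relevant values are graded by RCTC (Protocol 5.2.3). Treatment-emergence is counted from the first dose in the current study (SAP 10.2.1), so the baseline-grade condition does not apply, and events of Grade 3 or higher are to be described in detail (SAP 10.2.1.3). RCTC also has a Grade 4 for haemoglobin, which includes values below 7.0 g/dL. A value of 55 g/L is 5.5 g/dL and would meet it. This stands in large part: a reader might infer that such a relapse appears in no planned output, and the documents do not support that. But the route rests largely on investigator judgement, and the RCTC table in Protocol 10.3 has no row for albumin.

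**Highlighted values.** Protocol 7.3.3 says out-of-range and clinically relevant values will be highlighted in listings, without a baseline condition. SAP 6.2 refers to data listings in general, but the SAP's laboratory section does not carry the highlighting over.

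**Haemoglobin and albumin.** A reader might also infer that these two can never enter the listing. They can: any patient with baseline Grade 0 to 2 is listed on reaching Grade 3.

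**Conclusion.** The point holds for one defined group: patients already at Grade 3 for a parameter at the pre-risankizumab feeder baseline who recover and then relapse to Grade 3 in M15-989. For them the graded listing is silent in 15 of 19 parameters without cover from another laboratory listing. For haemoglobin and albumin it stays silent however low the value falls. For everyone else the listing works as intended.

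The number of patients is unknown. The documents do not give the count at Grade 3 or higher at feeder baseline. If it were 2% to 5% of 60 (an assumption with no source in the documents), it would be 60 × 0.02 = 1.2 to 60 × 0.05 = 3.0 patients. A reader might take this as the number missed. It is only the number at risk: to be missed, a patient must also recover, relapse in the same parameter, stay below Grade 4 where one exists, and fall outside the four liver tests. Some of those missed by the listing would still be reported as adverse events. The number may be zero.

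This is a gap in one safety listing. It is worth closing because the primary objective is long-term safety, single cases matter at this sample size, and the change is small.

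**What to change.** In SAP 10.3.2, drop the baseline-grade condition as a criterion for entering the listing and use it as a flag. List every subject with a CTC Grade 3 or higher value after the first M15-989 dose. For each, show the feeder-baseline grade and the grade of the last value before the first M15-989 dose, and flag worsening when the on-study grade exceeds either one, stating which.

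Every subject whom the present rule lists for a value after the first M15-989 dose stays listed. The patient with 78, 125 and then 75 g/L is added and flagged against extension entry. A patient at Grade 3 at both reference points and on study is listed without a flag, so persistent and recurrent abnormality can be told apart.

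The cost is a short SAP edit, one more column and a slightly longer listing. No new data are collected and the drug-free baseline is retained.
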